4 STUDY POPULATION

4.1 Study Population

A total of 500 subjects with T1DM are planned to be randomized in this study, to receive MYL-1601D or NovoLog® with a randomization ratio of 1:1.

A detailed description related to sample size determination is provided in [Section 7](#).

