5 SAMPLE SIZE AND POWER

Approximately 500 subjects with type 1 diabetes will participate in this trial. The sample size estimation is based on primary objective - to demonstrate that immunogenicity as assessed by TEAR rate with MYL-1601D is equivalent to that of NovoLog® during 24-week treatment. The 80% power will be achieved with 250 subjects per treatment arm to demonstrate that 90% confidence interval of treatment difference (MYL-1601D minus NovoLog®) is within prespecified \pm margin (Table 2 of the SAP) (Chow SC et al, 2002; Chow S-C et al 2003). The pre-specified equivalent margin is dependent on the final rate of NovoLog® TEAR rate. No replacement of subject will be performed if subject discontinued prematurely from the study.

Table 2: Margins and 95% CIs with different reference TEAR event rates in 500 subjects

Event Rate for Reference Product	Estimated 95% CI for the Event Rate (n=250)	Margin	Type I error 2 one-sided alpha	Power	Total N
5%	(2%,8%)	5.7%	0.05	80%	500
10%	(6%,14%)	7.9%	0.05	80%	500
15%	(11%,19%)	9.3%	0.05	80%	500
20%	(15%,25%)	10.5%	0.05	80%	500
25%	(20%,30%)	11.3%	0.05	80%	500
30%	(24%,36%)	12.0%	0.05	80%	500
35%	(29%,41%)	12.5%	0.05	80%	500
40%	(34%,46%)	12.8%	0.05	80%	500
45%	(39%,51%)	13.0%	0.05	80%	500
50%	(44%,56%)	13.1%	0.05	80%	500
55%	(49%,61%)	13.0%	0.05	80%	500
60%	(54%,66%)	12.8%	0.05	80%	500

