8.7.1 Analysis methods

Definition of Primary Endpoints

The TEAR rate during 24-week treatment period is the primary endpoint for this study. TEAR is defined as either one of the following:

- 1) Subjects who are ADA negative at baseline and become positive at any timepoint post baseline.
- 2) Subjects who are ADA positive at baseline and demonstrate 4-fold increase in titer values at any timepoint post baseline visit.

Although differences in TEAR rate is the primary endpoint for the study from a statistical perspective, given that immunogenicity is not a standard endpoint in clinical trials, this difference, even if significant, will not be assessed in isolation but will be part of totality of evidence including changes in HbA1c, FBG, insulin dose, neutralizing antibodies and injection site reactions to ensure that changes in TEAR rate, if any, are clinically correlated and meaningful.

Statistical Methodology for Primary Endpoint

The 90% confidence interval of the treatment difference (MYL-1601D minus NovoLog®) in the TEAR rate will be established using the Wald confidence limit method with multiple imputation (Section 8.7.2.1). The MYL-1601D TEAR rate will be declared equivalent to that of NovoLog® during the 24-week treatment period if the 90% confidence interval of the treatment difference in TEAR rate is within the pre-specified margin as displayed in Table 2 of the study SAP, as suggested by Chow et al. (2002; 2003). For specific reference drug rate-based margin calculation, please refer to the SAS example code in Section 10 (Appendices – SAS Example Codes).

The primary analysis will be based on the ITT population. In addition, all post-discontinuation and rescue data will be included in the analysis.

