8.7.2 Analysis of primary efficacy endpoint(s)

The primary objective of the study is to assess whether MYL-1601D is equivalent to NovoLog® in immunogenicity, as assessed by the rate of treatment emergent antibody response (TEAR) during 24 weeks of treatment. The primary efficacy endpoint is the TEAR rate at Week 24. TEAR is defined as either one of the following:

- 1) Subjects who are ADA negative at baseline and become positive at any timepoint post baseline
- 2) Subjects who are ADA positive at baseline and demonstrate 4-fold increase in titer values at any timepoint post baseline visit.

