8.7.2.1 Primary efficacy analysis

The primary efficacy analysis will be a test of equivalence for the MYL-1601D and NovoLog® groups in the TEAR rate at Week 24. The null hypothesis is non-equivalence, expressed by

$$H_0: |p_M - p_N| \geq \delta, \delta > 0$$

where p_M and p_N are the (true) proportions of subjects with TEAR in the MYL-1601D and NovoLog[®] groups, respectively, and δ is the equivalence margin. The null will be rejected in favor of equivalence if the 90% confidence interval of the treatment difference is within the range $(-\delta, \delta)$. The confidence interval as defined by Chow and Shao (2002) is constructed as

$$CI_{2\alpha} = [\hat{p}_M - \hat{p}_N - t_\alpha \hat{\sigma}, \hat{p}_M - \hat{p}_N + t_\alpha \hat{\sigma}]$$

where \hat{p}_j is the estimate of the TEAR rate p_j in each treatment group, $j \in \{M, N\}$, $\hat{\sigma}$ is the sample estimate of the standard error of the mean, and t_α the 0.05 quantile of the t distribution with $(N - 2)$ degrees of freedom with N being the pooled number of subjects in the analysis. That is, H_0 will be rejected if neither $-\delta$ nor δ is contained within the 90% confidence interval.

To minimize any bias due to missing data, the primary efficacy analysis will use multiple imputation to fill in missing ADA values. Multiple imputation (MI) will be applied to two measured variables: ADA binary response (positive/negative) and ADA continuous titer values. Multiple imputation will be done for each variable separately, then the two sets of imputed datasets will be merged in order to generate the imputed TEAR status. For subjects who are ADA negative at baseline, post-baseline missing values will be imputed using the binary response values obtained from logistic regression MI. Missing post-baseline values for subjects who are ADA positive at baseline will be derived from the continuous MI model. The primary efficacy analysis is based on the Week 24 (Visit 15) value. Subjects who discontinue treatment prematurely will be classified based on whether ADA values were obtained for the visits after treatment discontinuation (retrieved dropouts) or not.

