For continuous-valued ADA titer, missing values prior to the last observed visit will be filled in with MCMC imputation to make the dataset monotone. Missing values after discontinuation will be imputed by regression imputation of the monotone missing dataset. If there are at least 6 retrieved dropouts in each treatment arm, then a pattern mixture model estimated from the retrieved values will be used for regression imputation of missing values. Otherwise, the complete case missing values method will be used. Missing values for the binary response variable will be imputed using a logistic regression multiple imputation model. A monotone missingness pattern will be created by taking a random draw from the binomial distribution with the same probability as the observed responses from the same treatment group at the same visit.

Pattern mixture models will be fit separately for ADA binary response and for ADA titer. Binary response will be imputed using a logistic regression imputation model, while ADA titer will use a continuous-valued regression. Independent variables in the regression will include the values at all prior visits. Each imputation will be repeated 30 times with a seed of 40872021 for ADA binary response and a seed of 41671703 for ADA titer. Code for the multiple imputation analyses is presented in Appendix 10.1.

If baseline value is missing, the missing baseline value will be imputed with six imputations based on binomial distribution using probability of no missing baseline values from same treatment group.

After imputation, the dataset containing the imputed visitwise TEAR positive or negative status binary response and the dataset containing the imputed ADA titer values will be merged by subject, visit, and imputation number. The Week 24 values will then be used to assign the status of TEAR positive or negative, as follows:

If the subject was ADA negative at baseline, then this subject will be considered TEAR positive if any post-baseline observed or imputed value was ADA positive; otherwise, the subject will be considered TEAR negative. The imputed titer values will not be considered in subjects who are ADA negative at baseline.

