10.1.3 Combining the multiple imputation results to derive TEAR status

At this point there should be two sets of imputed data, each containing 30 records per subject, with all visits on the same record. These will need to be merged by subject and imputation. Then the TEAR values will be computed for each subject and analyzed. There are 3 steps:

1. Merge the imputed ADA binary response dataset with the imputed ADA titer dataset, by `usubjid avisitn _imputation_`. Then generate TEAR responder status based on the Week 24 (Visit 15) ADA values using the same algorithm as was used for the original data. This dataset will have one record per imputation per subject, but the TEAR values will be non-missing for all subject visits. Note that the variable TEAR may vary from imputation to imputation for the same subject. That is supposed to happen.
2. Run the primary efficacy analysis to create the 90% confidence interval using the Wald confidence limit method within each imputation. That will result in 30 confidence intervals, one for each imputation.
3. Combine the 30 confidence intervals to generate one summary confidence interval to be presented in the table.

Step 1.

Merge the imputed titer values by `usubjid avisitn _imputation_` to make a single dataset. Then create a new variable for TEAR status by following the ADaM specs for the definition of TEAR events, but using the new imputed ADA data. Again, the dataset will contain one record per imputation per subject, with a new response variable added to every record. For the purposes of the next steps below, this new response variable will be called TEAR.

- a. If the subject was ADA negative at baseline then do:
 - i. If any of RESP8–RESP15 is positive, then TEAR=1 for that imputation for that subject
 - ii. Else TEAR=0 for that imputation for that subject
- b. Else if subject was ADA positive at baseline then do:
 - i. If $ADA_x / ADA_0 \geq 4$ for any visit, where x is in 8–15, then TEAR = 1;
 - ii. else TEAR=0

Step 2.

Use code similar to what was used to analyze the primary efficacy endpoint, but run the code by `_imputation_`. For example,

```
/** step 2: Analyze the imputed datasets */  
proc freq data=imputed;  
by _imputation_;  
table trt*tear / alpha=0.10 riskdiff (cl= wald column=2)  
;  
output=outmi riskdiff;  
run;
```

Step 3.

Combine the 30 estimated statistics into one using PROC MIANALYZE.

```
proc mianalyze data=outmi;  
modeleffects _rdif1_ ;  
stderr e_rdif1;  

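### Three SAP sentences tie the primary TEAR analysis to the Week 24 value, against the any-visit definition in the protocol and in every SAP derivation rule

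*SAP*

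**What the plan says.** **Any post-baseline visit.** Protocol 3.2.1 and 7.2.1 and SAP 4.1, 8.7.1 and 8.7.2 share the same two-part definition. Its first part reads "Subjects who are ADA negative at baseline and become positive at any timepoint post baseline". The second part applies the same any-time rule to a 4-fold titer rise in subjects who are ADA positive at baseline. The classification rules near the end of the imputation text in SAP 8.7.2.1, and items a and b under Step 1 of SAP 10.1.3, carry this out. For baseline-negative subjects the appendix says: "If any of RESP8–RESP15 is positive, then TEAR=1 for that imputation for that subject".

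**Week 24 values.** SAP 8.7.2.1 says "The primary efficacy analysis is based on the Week 24 (Visit 15) value" and, after describing the merge of the imputed datasets, "The Week 24 values will then be used to assign the status of TEAR positive or negative". Item 1 of the three-step list that opens SAP 10.1.3 likewise generates responder status from the Visit 15 ADA values.

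**Looser Week 24 wording.** SAP 8.7.2 says "The primary efficacy endpoint is the TEAR rate at Week 24". The opening sentence of 8.7.2.1 tests the rate at that time point, and sensitivity analysis 2 in 8.7.2.2 imputes status at that time point.

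**Visitwise TEAR.** SAP 8.7.2.3 defines TEAR at a specific visit (vTEAR) as a separate summary.

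**The concern.** Antibody samples are taken at seven post-baseline visits (8, 9, 10, 11, 12, 13 and 15). A subject who is positive at Week 8 and negative at Week 24 is a responder under the definition, but not under a rule that uses the Visit 15 value. The contradictory sentences sit in the section that governs the primary analysis and in the appendix from which it will be programmed.

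Two results depend on the rule: the estimated difference in TEAR rates and the equivalence margin, because SAP 5 and 8.7.2.1 make the margin a function of the final NovoLog TEAR rate. A programmer who followed the Visit 15 sentence for one of these and the any-visit rule for the other would also break the link between margin and standard error on which the planned power rests.

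**Working it through.** **1. The passages side by side**

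| Place in SAP | Timing sentence | Any-visit rule in the same section? |
|---|---|---|
| 8.7.2 | rate at Week 24 | yes, numbered items 1 and 2 |
| 8.7.2.1, opening | test of rate at Week 24 | yes, later in the section |
| 8.7.2.1, imputation text | Week 24 (Visit 15) value | yes, later in the section |
| 8.7.2.1, after the merge | Week 24 values assign status | yes, directly after it |
| 8.7.2.2, item 2 | status at Week 24 imputed | not for the primary status |
| 10.1.3, item 1 of the list | Visit 15 ADA values | yes, items a and b |

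Rows 1, 2 and 5 can be read as cumulative status by Week 24. Rows 3, 4 and 6 cannot easily be read that way, because they name the values of one visit.

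**2. Inputs for the margin**
- Error rate: two one-sided tests at 0.05 (SAP Table 2, column "Type I error 2 one-sided alpha").
- Size and power: "The 80% power will be achieved with 250 subjects per treatment arm" (SAP 5).
- Allocation: "with a randomization ratio of 1:1" (Protocol 4.1).
- Formula (SAP 8.7.2.1): margin = (z_alpha + z_beta) × sqrt(2p(1−p)/n), where p is the NovoLog rate and n = 250.
- Quantiles: the code in SAP 10.2 uses the 0.95 and 0.90 normal quantiles, so the multiplier is 1.645 + 1.282 = 2.927.

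**3. Reproducing SAP Table 2**

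For rates of 5% to 60% in steps of 5%, the formula gives 5.70, 7.85, 9.35, 10.47, 11.33, 11.99, 12.48, 12.82, 13.02, 13.09, 13.02 and 12.82 points. All twelve agree with the table to within 0.05 points. The 0.80 quantile in place of 0.90 does not reproduce it (11.12 at 50%, where the table has 13.1).

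**4. Effect of the two rules on the margin**

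A subject who meets the criteria at Visit 15 also meets them at some visit. The Week 24 rate is therefore at most the any-visit rate, and lower only if some responses are transient. The documents give neither rate, so the rates below are assumptions.

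| Any-visit rate | Share still met at Week 24 | Week 24 rate | Margin, any visit | Margin, Week 24 |
|---|---|---|---|---|
| 20% | 100% | 20% | 10.5 | 10.5 |
| 10% | 75% | 7.5% | 7.9 | 6.9 |
| 20% | 75% | 15% | 10.5 | 9.3 |
| 30% | 75% | 22.5% | 12.0 | 10.9 |
| 20% | 50% | 10% | 10.5 | 7.9 |
| 30% | 50% | 15% | 12.0 | 9.3 |
| 50% | 90% | 45% | 13.1 | 13.0 |
| 60% | 75% | 45% | 12.8 | 13.0 |

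For example, at 20% the margin is 2.927 × sqrt(2 × 0.20 × 0.80/250) = 2.927 × 0.0358 = 10.5 points. At 15% it is 2.927 × sqrt(2 × 0.15 × 0.85/250) = 2.927 × 0.0319 = 9.3 points.

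For any-visit rates of 10% to 40% and persistence of 50% to 90%, the margins differ by about 0.3 to 2.7 points.

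**5. Power**

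With equal true rates, power = 2Φ(margin/SE − 1.645) − 1.
- Either rule used throughout: margin/SE = 2.927, so power is 80%.
- Any-visit rate of 20% (SE 3.58 points) against the margin for a 15% Week 24 rate: 9.35/3.58 = 2.61, so power is about 67%.
- The reverse (SE 3.19 points): 10.47/3.19 = 3.28, so power is about 90%.

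**The case against.** The strongest reply is that TEAR has only one definition. Every rule that classifies a subject uses any post-baseline visit, and no rule or code derives primary TEAR from Visit 15 alone. The Week 24 sentence after the merge leads straight into the any-visit algorithm. SAP 7.2.1 does not count a subject with partial data as missing once TEAR has been met, which makes sense only under the any-visit rule. This stands. It shows which text is right and limits the problem to wording, but it does not reconcile a sentence that bases the primary analysis on the Visit 15 value.

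Three stronger readings are tempting, and the documents do not support them:
- **That the choice of endpoint is left open until the data are seen.** Protocol 3.2.1 and 7.2.1 have only the any-visit definition, protocol section 7 ties a major change of the primary endpoint or its analysis to a protocol amendment, and the SAP writes out the any-visit derivation twice.
- **That the two rules must give different margins.** The rates coincide if no response is transient. The margin is also symmetric about 50%: Table 2 has 12.8 at both 40% and 60%, and 12.8 to 13.1 between them.
- **That any gap in sampling makes a subject missing under the any-visit rule.** SAP 7.2.1 says otherwise: the gap matters only if TEAR status cannot be determined.

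**Conclusion.** The contradiction is real and is in current SAP text. Three sentences conflict with the definition and three more are loose. The intended endpoint is clear from the protocol and the derivation rules, so this is a correction to stated rules for the primary analysis, not a dispute between two endpoints.

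If the Visit 15 sentences were applied, transient responders would be dropped. How much that matters cannot be known from the documents, because it depends on the NovoLog rate and on how many responses persist. Under the assumptions shown, the margin would move by anything from nothing to about 2.7 points. Power under equal rates would stay at 80% provided one rule served both the interval and the margin. The correction should be made because it concerns the primary endpoint and costs little.

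**What to change.** In the SAP:
- **8.7.2.1, sentence on the Visit 15 value:** delete it, or replace it with: *The primary efficacy analysis is based on cumulative TEAR status, i.e. TEAR criteria met at one or more post-baseline sampling visits through Week 24.*
- **8.7.2.1, sentence after the merge, and 10.1.3, item 1 of the opening list:** refer to *observed and imputed values at all post-baseline visits through Week 24* in place of the Week 24 values.
- **8.7.2, the opening sentence of 8.7.2.1, and 8.7.2.2 item 2:** change the Week 24 timing to the 24-week treatment period, as in SAP 4.1.
- **Margin text in 8.7.2.1:** state that the margin uses the NovoLog TEAR rate on this same cumulative definition.
- **Week 24 TEAR:** keep it only as the Visit 15 entry in the vTEAR summary.

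The cost is a few sentences. The protocol definition, Table 2, the sample size of 500 and the classification rules stay as they are, and no new data are needed.

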7.2 Handling of missing data and outliers

7.2.1 Missing data analysis methods

Missing data will only be imputed in the primary and sensitivity analyses for TEAR rate associated with ADA and other secondary variables that are mentioned in this document. Otherwise, missing data will not be imputed.

Subjects with missing data are either 1) subjects who completely miss post-baseline ADA data or 2) subjects who miss a portion of ADA data and for whom the TEAR positive or negative status cannot be determined. If a subject with partially missing ADA data already

meets the TEAR criteria, the subject is not considered to be a subject with missing data. To minimize any bias due to missing data, multiple imputation will be used to fill in missing values according to either of two TEAR criteria (binary response and continuous titer values) prior to deriving the TEAR and subsequently estimating the treatment difference and 90% confidence interval. Two imputation processes will be used for each of two TEAR criteria among the missing data. For baseline ADA negative subjects, post baseline binary response (positive or negative) will be imputed using logistic regression multiple imputation assuming missing not at random. For baseline positive subjects, missing titer values (continuous values) will be imputed with same treatment group non-missing subjects using pattern mixture model with the complete-case missing values (CCMV) method (Little 1993). In the case where there are sufficient number of retrieved dropouts, that is, if there are 6 retrieved dropout subjects in each treatment group, the missing values in that treatment group will be imputed by modelling the retrieved subgroup data. Retrieved dropout subjects are the subjects who discontinued assigned study treatment but still remain on the study and had their efficacy and safety measurements captured at the planned visits. If less than 6 retrieved dropout subjects in each treatment group, all non-missing subjects within same treatment group will be used to impute missing data by multiple imputation.

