10.1 Multiple imputation

Multiple imputation will be applied to fill in missing values for ADA binary response and for ADA titer.

For binary ADA response, if baseline ADA value is missing, the missing baseline value will be imputed (6 imputations) based on binomial distribution using probability of no missing baseline values from the same treatment group. After imputations, for subjects with negative baseline ADA (Section 10.1.1) missing post-baseline binary response (positive or negative) will be imputed using logistic regression multiple imputation. For subjects who are ADA positive at baseline (Section 10.1.2), missing post-baseline ADA continuous titer values will be imputed with same treatment group non-missing subjects using continuous MI model.

The steps are summarised below:

Section 10.1.1 describes the methodology for imputation of binary response, while Section 10.1.2 covers the imputation of continuous ADA titer, and Section 10.1.3 puts them together.

10.1.1 Multiple imputation for binary ADA response if baseline ADA is negative.

For purposes of these specifications, let $RESP_x$ represent the binary value (0 or 1) at Visit x , where x takes the values 0 (for Baseline) or 8–15. The seed that will be used in the multiple imputation of ADA binary response will be 40872021.

Missing values will be obtained from logistic regression imputation on the observed values of binary response. A fully conditional specification (FCS) method will be used to impute values from a non-monotone missing data pattern.

There are 3 steps to this process:

1. Create a dataset with one record per subject, containing all values of $RESP$ for all weeks (Baseline and Weeks 2–24 on one record); that is, each record would contain variables for $RESP_0$ and $RESP_8$ – $RESP_{15}$. The subject-level $RETRIEVED$ variable described in Section 8.7.2.1 can also be generated at this time for subjects who discontinued treatment, based on whether values after treatment discontinuation

- were retrieved (set retrieved=1) or remain missing (set retrieved=0).
2. Fill in missing values to make a monotone missing data pattern, by drawing random TEAR values from the binomial distribution based on the TEAR frequencies for the given visit within treatment group.

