 3. Run a pattern mixture model logistic regression to impute missing values to generate 30 imputed datasets. This will generate a single pooled dataset containing one observation per subject per imputation. All missing values will have been filled in for each subject.

Step 1.

The dataset for this imputation has to put the values for all weeks onto one record. That is, the dataset would have one record per subject, with 8 values for RESP0 and RESP8–RESP15. One way this can be accomplished is the following:

```
data analysis (keep=usubjid RESP0 RESP8-RESP14);
set indata;
by usubjid avisitn;
array R {9} RESP0 RESP8-RESP15;
retain RESP0 RESP8-RESP15;
if first.usubjid then do;
    resp0 = base;
    do visit = 8 to 15;
        R{visit} = .;
    end;
end;
do visit = 8 to 15;
    if avisit = visit then R{visit} = aval;
end;
if last.usubjid then output;
run;
```

STEP 2.

First a flag needs to be created to indicate which missing values need to be filled in. This is a visit-level variable for each subject. For explanatory purposes, this variable will be referred to as EMPTY_x for Visit x. For each visit where a subject has a missing value, use the logic below:

- If there is a non-missing value for any visit AFTER Visit x, then EMPTY_x=0;
- Else if there are no non-missing values for any of the remaining visits, then EMPTY_x=1;

Then all records with EMPTY_x=1 have to have their RESP_x value filled in with a randomly generated 0 or 1. One way this can be accomplished is the following:

```
/** step 2: Make missingness monotone */  
%global mylrate novrate;
```

```
%macro getrate(visnum);
```

```
    proc sort data=indata;  
        by trtgroup;  
    run;  
    ods exclude all;  
    proc freq data=indata;  
        by trtgroup;  
        table RESP&visnum;  
    ods output onewayfreqs=pct;  
    run;  
    ods exclude none;
```

```
    data binom;  
        set pct (where=(RESP&visnum=1));  
        probresp = percent/100;  
        if trtgroup="MYL-1601D" then call  
            symput("mylrate",probresp);  
        else if trtgroup="NOVOLOG" then call  
            symput("novrate",probresp);  
    run;
```

```
%mend getrate;
```

```
%macro fillin (visit);
```

```
    %getrate(&visit);
```

```
    data indata;  
        set indata;  
        if empty&visit=1 then do;  
            if trtgroup="MYL-1601D" then  
                RESP&visit=ranbin(86537043,1,&mylrate);  
            else if trtgroup="NOVOLOG" then  

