                RESP&visit=ranbin(48010557,1,&novrate);
```

```
end;  
run;
```

```
%mend fillin;
```

```
%macro monotone;  
  %do vis=8 %to 13;  
    %fillin(&vis);  
  %end;  
%mend monotone;
```

```
%monotone;
```

STEP 3.

Since SAS will not accept a binary variable as an independent variable in a logistic imputation model, continuous versions of the binary RESP variables. Both the continuous and categorical variables will be used during the regression. In the code below, the logistic regression code is different If there are <6 retrieved dropouts per group versus ≥ 6 .

```
/***/ setup: create numeric versions of binary variables  
***/  
data indata;  
set indata;  
array resps {7} resp0 resp8-resp14;  
array respns {7} respn0 respn8-RESPN14;  
do i=1 to 7;  
  respns{i} = resps{i};  
end;  
run;
```

```
/** step 3: Perform logistic regression imputation */  
  
/** Code to use if >=6 retrieved subjects per arm */  
proc mi data=indata nimpute=30 seed=40872021  
out=outdata;  
class resp8-resp15;  
var resp0n resp8 resp8n resp9 resp9n resp10 resp10n  
resp11  
    resp11n resp12 resp12n resp13 resp13n resp14 resp14n  
resp15;  
monotone logistic (resp8= resp0n) ;  
monotone logistic (resp9= resp0n resp8n) ;  
monotone logistic (resp10= resp0n resp8n resp9n) ;  
monotone logistic (resp11= resp0n resp8n resp9n resp10n)  
;  
monotone logistic (resp12= resp0n resp8n resp9n resp10n  
resp11n) ;  
monotone logistic (resp13=  
    resp0n resp8n resp9n resp10n resp11n resp12n) ;  
monotone logistic (resp14=  
    resp0n resp8n resp9n resp10n resp11n resp12n resp13n)  
;  
monotone logistic (resp15=  
    resp0n resp8n resp9n resp10n resp11n resp12n resp13n  
resp14n) ;  
mnar model (resp8-resp15 / modelobs=(retrieved=1));  
run;
```

```
/** Code to use if <6 retrieved subjects per arm */
proc mi data=indata nimpute=30 seed=40872021
out=outdata;
by trtgroup;
class resp8-resp15;
var resp0n resp8 resp8n resp9 resp9n resp10 resp10n
resp11
    resp11n resp12 resp12n resp13 resp13n resp14 resp14n
resp15;
monotone logistic (resp8= resp0n) ;
monotone logistic (resp9= resp0n resp8n) ;
monotone logistic (resp10= resp0n resp8n resp9n) ;
monotone logistic (resp11= resp0n resp8n resp9n resp10n)
;
monotone logistic (resp12= resp0n resp8n resp9n resp10n
resp11n) ;
monotone logistic (resp13=
    resp0n resp8n resp9n resp10n resp11n resp12n) ;
monotone logistic (resp14=
    resp0n resp8n resp9n resp10n resp11n resp12n resp13n)
;
monotone logistic (resp15=

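### The SAP fills gaps in the binary ADA record with a random draw that ignores the subject's own results and is not restricted to baseline-negative subjects, though one imputed positive makes a TEAR responder

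*SAP*

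**What the plan says.** **The fill.** SAP 8.7.2.1 creates a monotone pattern for the binary ADA response by "a random draw from the binomial distribution with the same probability as the observed responses from the same treatment group at the same visit". Gaps in titer are instead filled by MCMC, which uses the subject's other values.

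**The endpoint rule.** For a subject who is ADA negative at baseline, "this subject will be considered TEAR positive if any post-baseline observed or imputed value was ADA positive" (SAP 8.7.2.1). SAP 7.2.1 counts as missing those "subjects who miss a portion of ADA data and for whom the TEAR positive or negative status cannot be determined". A never-positive subject with one missed sample is such a case.

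**The appendix.** SAP 10.1.1 is headed "Multiple imputation for binary ADA response if baseline ADA is negative". It says that "A fully conditional specification (FCS) method will be used to impute values from a non-monotone missing data pattern", but its Step 2 then fills by "drawing random TEAR values from the binomial distribution based on the TEAR frequencies for the given visit within treatment group". The Step 2 code takes the rate from `PROC FREQ` by treatment group ("table RESP&visnum;") with no filter on baseline status. The Step 3 code uses baseline status as a predictor ("monotone logistic (resp8= resp0n").

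**The margin.** SAP 8.7.2.1 sets the equivalence margin as a function of the NovoLog TEAR rate.

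**The concern.** TEAR is decided by any one positive among seven post-baseline samples (Visits 8 to 13 and 15). A fill rule for a single cell is therefore a rule for the endpoint. An otherwise all-negative subject with one gap becomes a responder with probability equal to the draw rate, whatever the neighbouring results show.

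If the rate is taken from the whole arm, it includes subjects who were already ADA positive at baseline. The binary value decides TEAR only for baseline-negative subjects, so they would be given a positivity rate that is largely not theirs. False responders added to both arms dilute a true difference. If the margin is set from the imputed NovoLog rate and that rate is below 50%, the margin widens as well. Both effects make a false declaration of equivalence easier.

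**Working it through.** **1. Reproduce the margin.** SAP Table 2 follows from the quantiles in the tipping-point code (0.95 and 0.90), with n = 250 per arm:

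δ = (1.645 + 1.282) × √(2p(1−p)/250)

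- p = 10%: 2.926 × √0.00072 = 7.85% (table 7.9%)
- p = 20%: 2.926 × √0.00128 = 10.47% (table 10.5%)
- p = 50%: 13.09% (table 13.1%)
- p = 60%: 12.82% (table 12.8%)

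All 12 rows agree within 0.05 points. The margin rises with the NovoLog rate up to 50% and falls after it.

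**2. Which rate is drawn?**

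| Points to the whole arm | Points elsewhere |
|---|---|
| The 8.7.2.1 sentence names only treatment group and visit | The 10.1.1 heading limits the section to baseline-negative subjects |
| `PROC FREQ` in Step 2 has no baseline filter | SAP 7.2.1, 8.7.2.1 and 10.1 split the two imputations by baseline status |
| Baseline status is a predictor in Step 3; it would be constant if only baseline-negative subjects were in the data | Step 2 text speaks of TEAR frequencies, not ADA responses |
| 8.7.2.1 sets imputed titers aside for baseline-negative subjects only when TEAR is derived | 10.1.1 names FCS for the non-monotone pattern, which would make the draw unnecessary |

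The whole-arm reading has more support in the operative sentence and code, but it is not settled.

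**3. Which cells are filled?** In Step 2, `EMPTY` is 0 when a later value exists and 1 when none does, and only cells with 1 are filled, at Visits 8 to 13. As coded, the draw goes to trailing gaps, the reverse of what makes a pattern monotone. With draw rate q and k filled cells, the chance of becoming a responder is 1 − (1−q)^k:

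| q | k = 1 | k = 3 | k = 6 |
|---|---|---|---|
| 0.05 | 5% | 14% | 26% |
| 0.40 | 40% | 78% | 95% |

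**4. Size, with the flag corrected to match 8.7.2.1.** The documents give no ADA or gap rates. Assumptions: 20-60% baseline positive, of whom 92% are positive at each later visit; 80% persistence after conversion; 2-5% of the six interim samples missed at random; the same TEAR rate in both baseline strata; one fill before the 30 imputations, as in the code.

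Hand check at 40% baseline positive, 5% missed, true TEAR 10%, and about 5% visitwise positivity in baseline-negative subjects (assumed):

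- Whole-arm rate: q = 0.40 × 0.92 + 0.60 × 0.05 = 0.398.
  - Baseline-negative TEAR: 0.10 + 0.90 × [1 − (1 − 0.05 × 0.398)^6] = 0.202.
  - Arm: 0.60 × 0.202 + 0.40 × 0.10 = 16.1%. Margin: 7.85% becomes about 9.6%.
- Baseline-negative rate: q = 0.05.
  - Baseline-negative TEAR: 0.10 + 0.90 × [1 − (1 − 0.05 × 0.05)^6] = 0.113.
  - Arm: 0.60 × 0.113 + 0.40 × 0.10 = 10.8%.

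Simulation over the full range, 250 per arm, 90% Wald interval, margin from the imputed NovoLog rate, MYL-1601D truly at the margin:

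| | Complete data | Whole-arm draw | Baseline-negative draw |
|---|---|---|---|
| Reported NovoLog TEAR, true 10% | 10% | about 12-16% | about 10.1-11.0% |
| P(equivalence), true 10% | about 7-8% | 10-18% | no material rise |
| P(equivalence), true 20% | about 6-7% | 8-12% | no material rise |

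The excess over 5% with complete data comes from setting the margin from observed data, which is a separate matter.

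**The case against.** The strongest objection is that the SAP repeatedly sends only baseline-negative subjects to the binary imputation, so the damaging whole-arm rate may never be used. The code is labelled as an example and cannot run as printed: for instance, a 7-element array is given 8 names. A leftover predictor in such code does not define a population. The flow chart in section 10 is not shown in the text reviewed and may settle the point. This stands, as far as it goes. A reader might infer from the operative sentence and the unfiltered `PROC FREQ` that baseline-positive subjects are certainly in the rate. The documents favour that reading but do not establish it.

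Two other inferences go too far:

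- **That one missed mid-record sample is filled by this draw as coded.** It is not, because the flag sends the draw to trailing gaps. The sizes above apply once the code is made to match 8.7.2.1.
- **That the fill always widens the margin.** It does so only through the NovoLog arm, only below 50%, and only if the imputed rate sets the margin; the SAP speaks just of the final rate. The confidence interval also widens as the rates rise.

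The inflation is also smaller if the draw is repeated within each imputation: about 9-13% false equivalence at a true 10%, and 6-8% at 20%.

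SAP 8.7.2.2 repeats the analysis on observed data without imputation, and in simulation that returned 9.9-10.0% at a true 10%. A large artefact would therefore be visible. It would not be cured, because the equivalence decision rests on the imputed data.

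**Conclusion.** The point holds in this form. The prescribed draw ignores the subject's own results on either reading of the rate, and no rule restricts its rate to the subjects whose endpoint it decides. The SAP also contradicts itself on the rate (ADA responses or TEAR frequencies), on the method (binomial draw or FCS) and on the cells to fill.

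The consequence ranges from a small upward bias in TEAR, if the rate comes from baseline-negative subjects, to roughly a doubling of the false-equivalence risk at the upper end of the whole-arm range (10% reference rate, 5% of samples missed). These sizes rest on assumed ADA and missed-sample rates, a corrected flag, a single fill, and a margin set from the imputed NovoLog rate. Because this is the primary analysis and the reading that matters is left open, it should be settled before unblinding.

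**What to change.** In SAP 8.7.2.1 and 10.1.1:

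1. Delete the binomial draw.
2. Restrict the binary imputation to subjects who are ADA negative at baseline, in both text and code.
3. Impute mid-record gaps within treatment group by FCS logistic regression on the subject's other sampled visits, inside the 30 imputations, as the appendix already indicates.
4. Then apply the planned missing-not-at-random step to values after dropout.
5. Correct the `EMPTY` flag so that mid-record and trailing gaps are not confused.
6. State which NovoLog TEAR rate, observed or imputed, sets the margin.

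The cost is SAP wording and a few lines of code, with no new data. The reported TEAR rate and the margin may come out slightly smaller.
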